3.1 Study design

This global, multicenter study will be conducted in a randomized, controlled, parallel-group, participant-blinded fashion in approximately 180 symptomatic adult CRS participants who have failed previous medical management. Participants enrolled in the study will include participants who have accessible and intact middle meatus. The efficacy and safety of LYR-210 matrix (7500 µg) versus a control group receiving a sham procedure will be assessed on a background therapy of daily saline irrigation. Participants will be randomized 2:1 to either treatment with LYR-210 or to control.

The study will consist of 3 stages:

- Screening and run-in stage: 2-4 weeks before randomization and treatment procedure
- Treatment stage (LYR-210 or control): randomization and treatment procedure through 24 weeks
- Safety extension: Weeks 25 through 52

A safety extension phase after the Week 24 visit will involve crossover for all control participants and treatment participants will be re-randomized 1:1 to either sham or a second round of active treatment with follow-up through Week 52. The study design is depicted in **Figure 1**.

[figure not shown]
[figure not shown]

Figure 1. Study Design.

3.2 Study size and duration

Approximately 180 participants are planned to be enrolled in this study.

The total duration of the study, including the enrollment period, is approximately 26 months.

The total duration of the study participation for all enrolled and treated participants is expected to be approximately 13 months (including the Screening/Run-in, Treatment, and Safety Extension stages). The end of the study (EOS) is defined as the date of the last EOS visit of the last participant of the study.

3.3 Study population

The study population will consist of approximately 180 adult participants with symptomatic CRS without nasal polyps or with grade 1 nasal polyps, who have failed previous medical management. Enrollment of participants with nasal polyps of grade 1 will be limited to approximately 30 participants.

3.3.1 Inclusion criteria

A participant must meet all the following criteria to be eligible for this study:

- 1. Age ≥ 18 .
- 2. Diagnosed as having CRS, defined by duration of 12 weeks or longer with 2 or more of the following symptoms:
 - nasal blockage/obstruction/congestion
 - nasal discharge (anterior, posterior, or both)
 - facial pain/pressure
 - reduction/loss of sense of smell
- 3. Bilateral ethmoid disease, defined as each side of anterior and/or posterior ethmoid sinus is ≥5% opacified upon the screening computed tomography (CT), as determined by the Central Imaging Core Lab/ Central Reviewer.
- 4. Mean 3CS score over the preceding 7 days ≥5 (0-3 scale for each of the symptoms) determined within 7 days of Day 1 (ie, the determination for eligibility can be made on any day from Day -7 through Day 1).
- 5. Undergone at least 2 trials of medical treatments in the past, 1 of which must include intranasal corticosteroid sprays (INCS) for a minimum of 4 weeks with written

- medical record or confirmed via patient report and documented in the medical report record and are no longer using INCS at Screening.
- 6. Has been informed of the nature of the study and has provided written informed consent as approved by the Institutional Review Board (IRB)/Ethics Committee (EC) of the respective clinical site or regulatory authority if applicable by national law.
- 7. Agrees to comply with all study requirements.
- 8. If currently on a waiting list for sinonasal surgery at the time of Screening, is willing to be removed from the waiting list or have a preplanned/elective sinonasal surgery date cancelled for the duration of the study. [Note: this does not preclude a participant from receiving or being recommended for sinonasal surgery as rescue treatment during the study]

3.3.2 Exclusion criteria

A participant who meets any of the following criteria will be excluded from this study:

- 1. Inability to tolerate topical anesthesia or endoscopic procedure.
- 2. Previous ethmoidectomy, or surgery of the middle meatus and/or middle turbinate preventing proper placement and retention of LYR-210. NOTE: any previous ethmoidectomy is exclusionary.
- 3. Previous nasal surgery or polypectomy within 3 months of Screening visit.
- 4. Presence of nasal polyps grade 2 or higher (ie, polyps extending outside the middle meatus) on either side.
- 5. Seasonal allergic rhinitis (SAR) with symptoms and/or, based on time of year, would anticipate onset of symptoms within 24 weeks of randomization. NOTE: mild SAR symptoms, as assessed by the Investigator, are not exclusionary.
- 6. Perennial rhinitis with symptoms that are well controlled by regular use of intranasal corticosteroids.
- 7. Severe asthma or experienced 1 or more exacerbations of asthma requiring SCS use within the 6 months prior to the Screening visit. Participants with moderate or severe asthma will also be excluded if they have not been on a stable regimen of inhaled corticosteroids for asthma for a minimum of 3 months prior to the Screening visit.
- 8. Endoscopic exclusion criteria at Screening or Day 1 visit:
 - a) Obstruction of middle meatus or degenerated middle turbinate preventing proper placement and retention of LYR-210.
 - b) Evidence of mucosal erosion or ulceration.
 - c) Acute nasal/sinus infection or purulence.
 - d) Evidence of nasal septal perforation.
- 9. Screening CT exclusion criteria:
 - a) Anatomic variation that, in the opinion of the investigator, would adversely impact placement of LYR-210.

- b) Structural, non-inflammatory related CRS (eg, large concha bullosa preventing proper matrix placement, tumor).
- c) Sinus disease extended into orbital or intracranial space.
- d) Evidence of mycetoma/fungal ball, allergic fungal rhinosinusitis.
- e) Sinus mucocele
- 10. History or clinical evidence or suspicion of invasive fungal sinusitis, allergic fungal rhinosinusitis, atrophic rhinitis, or odontogenic sinusitis.
- 11. Known history of hypersensitivity or intolerance to corticosteroids.
- 12. Oral steroid or monoclonal antibody (Xolair, Nucala, Dupixent, etc.) dependent condition, including biologics use within 3 months of screening and systemic steroid use within 1 month of screening. NOTE: monoclonal antibodies for this exclusion are limited to those that target T2 inflammatory pathway and/or are known to impact CRS-related inflammation and symptoms.
- 13. SCS administered within 1 month prior to Screening visit.
- 14. Known history of hypothalamic pituitary adrenal axial dysfunction.
- 15. Previous pituitary or adrenal surgery.
- 16. More than 1 episode of epistaxis with frank bleeding requiring medical attention within 2 months of Screening visit or more than 1 episode of epistaxis with frank bleeding within 1 month of Screening visit.
- 17. Acute exacerbation of nasal allergy or CRS, upper respiratory tract infection (URTI), or common cold within 4 weeks of the Screening visit. The infection/exacerbation must be resolved, and antibiotic or other medication use must be discontinued prior to screening.
- 18. Dental procedure/implant on maxillary dentition within 4 weeks of the Screening visit.
- 19. Past or present acute or chronic intracranial or orbital complications of CRS (eg, brain abscess, related problems with eyes or central nervous system).
- 20. History or diagnosis (in either eye) of glaucoma or ocular hypertension (IOP >21 mmHg).
- 21. Presence (in either eye) of posterior subcapsular cataract of grade 2 or higher, nuclear sclerosis of grade 3 or higher, or cortical cataract of grade 2 or higher or involving a minimum of center optic zone of 3-mm diameter.
- 22. Loss of functional vision in 1 or both eyes.
- 23. Diagnosed with ongoing rhinitis medicamentosa.
- 24. Known history of immune dysfunction including immune deficiency (IgG subclass deficiency or IgA deficiency) or autoimmune disease (eg, Wegener's granulomatosis, sarcoidosis) that requires immunomodulatory therapy. NOTE: Autoimmune conditions that do not require immunomodulatory therapy are not exclusionary.
- 25. Currently positive for COVID-19 or residual sinonasal symptoms from a previous COVID-19 infection within the past 6 months.

- 26. Past, present, or planned organ transplant, or chemotherapy with immunosuppression within the past 5 years.
- 27. History or diagnosis of ciliary dysfunction (eg, cystic fibrosis, primary ciliary dyskinesia [Kartagener syndrome]).
- 28. Past or present systemic vasculitis (eg, granulomatosis with polyangiitis).
- 29. Evidence of disease or condition expected to compromise survival or ability to complete follow-up assessments.
- 30. Pregnant or breast feeding. Females of child-bearing potential must test negative for pregnancy at the time of screening based on a serum pregnancy test and reverified at the time of enrollment based on a urine pregnancy test. Both male and female participants of reproductive potential must agree to use highly effective methods of birth control, throughout the study. (See **Appendix 14.3** for further information on contraception and pregnancy.)
- 31. Previously received an experimental treatment in another clinical study within 5 half-lives or 30 days (whichever is longer) of Screening visit or prior participation in another LYR-210 clinical trial.
- 32. Currently participating in an investigational drug or device study.
- 33. Determined by the investigator as not suitable for reasons not already specified if the health of the participant or the validity of the study outcomes may be compromised.

3.4 Concomitant medications

Participants in the study are free to use any appropriate concomitant medications if medically warranted per treating physician's discretion. However, a standardized concomitant medications regimen is recommended during the run-in and treatment stages to avoid confounding the efficacy or safety assessments of LYR-210. Effective treatment will not be withheld from study participants solely for entering the study.

3.4.1 Permitted medications

At the discretion of the investigator, the following concomitant medications may be used in accordance with the restrictions described for each treatment:

- All participants will be provided with saline and instructions for daily intranasal saline irrigation as background treatment starting from screening through Week 52/EOS.
- If acute sinus infection is suspected at any time during the study, treatment with antibiotics or macrolides (for a maximum of 14 days) will be allowed after a clinic visit and according to the investigator's judgment.
- For severe acute nasal blockage lasting a minimum of 3 consecutive days: a course of oxymetazoline nasal decongestant spray for a maximum of 3 consecutive days and a total maximum of 10 days during the treatment period. Oxymetazoline cannot be used within 24 hours before CT assessments.
- Nonsedating oral antihistamine including second (eg, loratadine, cetirizine), third (eg, fexofenadine), and fourth generation or equivalent.

- Participants who have been on a stable regimen of inhaled corticosteroids or leukotriene receptor antagonist for a minimum of 3 months prior to the Screening visit should remain on the same dosage throughout the study. Inhaled corticosteroid use must be limited to a stable low- or medium-dose as defined by guidelines established by the 2020 Global Initiative for Asthma Management and Prevention.¹⁰
- Participants who have been on a stable regimen of long- or short-acting beta agonists (LABA, SABA) for chronic obstructive pulmonary disease (COPD) or asthma for a minimum of 3 months prior to the Screening visit should remain on the same dosage throughout the study.
- Perennial allergic rhinitis (PAR) participants who have been on a stable regimen of a
 nonsedating oral or intranasal antihistamine including second (eg, loratadine, cetirizine,
 azelastine), third (eg, fexofenadine), and fourth generation or equivalent for a minimum
 of 3 months prior to the Screening visit should remain on the same dosage throughout the
 study.

3.4.2 Prohibited medications

Use of the following medications is prohibited for the duration of the study:

- Oral/ocular/intramuscular/intravenous/intranasal corticosteroids (except for oral corticosteroids as permitted for rescue medication only and stable low or medium dose of inhaled corticosteroids for underlying respiratory diseases, eg, COPD, asthma).
- Certain anti-allergy medications, including: first generation antihistamines (eg, diphenhydramine, dimenhydrinate, chlorpheniramine); leukotriene receptor antagonists (except for a stable regimen for asthma or another non-CRS indication), nasal cromolyn sodium or sodium cromoglycate, nedocromil sodium, atropine, ipratropium bromide, or guaifenesin.
- Oral or intranasal decongestants (except for short course of intranasal decongestants permitted for severe acute nasal blockage or one-time administration during endoscopic procedures).
- Inhaled anticholinergic medications (except for a stable regimen defined as no changes in the 3 months prior to screening and throughout study participation).
- Any potent cytochrome P-450 3A4 (CYP3A4) inhibitors (eg, ketoconazole and ritonavir).
- Any monoclonal antibody.
- Any allergen immunotherapy (except for a stable dose and regimen defined as no changes in the 3 months prior to screening and throughout study participation).
- Oral antifungal medication.

Participants who received prohibited medications will be considered to have a protocol deviation and may require withdrawal from the study.

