2.2 Study endpoints

2.2.1 Primary estimand/Primary efficacy endpoint

The primary estimand is a composite strategy. The attributes of the primary estimand are provided below in **Table 1**.

Table 1. Attributes of the Primary Estimand

Attribute	Specification
Treatment	LYR-210 7500 µg drug matrix over a 20-week period or sham procedure, with daily saline nasal irrigation
Population	Adults with CRS who do not have nasal polyps, have failed medical management (including treatment with intranasal corticosteroid sprays [INCS]), and have not had endoscopic sinus surgery (ESS)
Variable (Primary Endpoint)	The primary endpoint is change from baseline (CFBL) in the 7-day average composite score of the 3 cardinal symptoms (3CS) of nasal blockage/obstruction/congestion, anterior/posterior nasal discharge, and facial pain/pressure at Week 24 in participants without nasal polyps. The daily composite score is the sum of the 3 daily cardinal symptom scores. If less than 4 daily scores are available for a week, the 3CS score will be considered missing for the week.
Intercurrent Events	 (1) Rescue with systemic corticosteroids (SCS) or ESS: a composite variable strategy will be implemented where the 3CS score post SCS use or ESS will be censored and imputed with the participant's worst observed score. (2) Use of decongestants: a treatment policy strategy will be adopted in which the 3CS scores reported by the participants will be used regardless of whether decongestants have been used. (3) Use of INCS: INCS use is prohibited during both the washout and treatment periods per the protocol. If the use of INCS occurs in violation of the protocol, a treatment policy strategy will be used. (4) Infection with COVID-19: a hypothetical strategy will be used in which the 3CS score reported by the participants will be used as if the COVID-19 infection never occurred. (5) Spontaneous dislodgement of LYR-210 drug matrix: a treatment policy strategy will be used in the event of spontaneous drug matrix dislodgement.
Population-level Summary for the Variable	Mean change from baseline in the 3CS score at Week 24

See Section 9 (Statistical Considerations) for the primary analysis method.

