3.5.10 Discontinuation of Study Participants

Each subject is free to discontinue from the study at any time, for any reason, and without penalty or loss of benefit. Participation in the study treatment may be discontinued for any of the following reasons:

• Occurrence of any medical condition or circumstance that exposes the subject to substantial risk and/or does not allow the subject to adhere to the requirements of the protocol, including early removal of LYR-210

- Any serious AE (SAE, Section 7.2), clinically significant AE, severe laboratory abnormality, intercurrent illness, pregnancy, or other medical condition that indicates to the Investigator that continued participation is not in the best interest of the subject.
- Subject's decision to withdraw
- If deviations to the use of prohibited medications occur after randomization and study treatment, the Investigator in consultation with the Sponsor and Sponsor's medical monitor will decide on a case-by-case basis whether the subject may continue in the study based on the time the prohibited medication was administered and its pharmacology.
- Subject's failure to comply with protocol requirements or study related procedures.
- Termination of the study by the Sponsor or a regulatory authority that has provided approval to proceed.

Subjects who withdraw or are withdrawn from the study treatment will be requested to return to the clinic for the assessments and procedures scheduled for the end of treatment visit and the safety follow up visits (Section 3.5.9). The Investigator or study staff will document the reason(s) for subject discontinuation on the Case Report form (CRF) and notify the IRB/EC as required by their Institution's procedures.

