7.10 Safety monitoring

Participants will be closely monitored throughout the trial with high priority for participant safety. The sponsor will establish a Safety/Medical Monitoring team early in the study. The team will be responsible for developing a Safety/Medical Monitoring Plan (MMP) which will define in detail the objectives, scope, and roles and responsibilities of each team member involved.

Participant safety monitoring encompasses, but is not limited to, providing advice to sites and the project team for protocol-related issues, providing input into decisions requiring medical advice and routine safety monitoring of the study, review of serious and nonserious AEs, various data listings, lab results, vital signs, and other clinical data. Reviews of blinded aggregate data as well as individual participant data may be undertaken to identify outliers and trends that may impact safety of the participant and consistency of data.

8. Protocol Deviations

The investigator agrees to conduct the study according to the clinical protocol, local regulatory authority regulations, GCP, and any conditions of approval imposed by their IRB/EC and agrees that all persons delegated to perform study procedures will do so as well.

A protocol deviation is a failure to comply with the requirements specified within this clinical study protocol. Examples of protocol deviations may include enrollment of a study participant who does not meet all the inclusion/exclusion criteria specified in the protocol, use of prohibited medications or therapies, visits performed outside of the protocol-specified visit window, and missed study assessments or visits. All protocol deviations should be documented and explained. Major/CSR reportable protocol violations are defined as those that could impact the performance evaluation such as enrollment of an ineligible participant, missing key data, administration of an unauthorized treatment. All participants with protocol deviations will continue to be followed for safety and performance assessments unless sponsor determines that the participant should be discontinued from the study.

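### The protocol allows withdrawal from the study for prohibited-medication use, while the primary estimand needs the later 3CS scores of INCS and decongestant users

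*Protocol*

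**What the plan says.** **The withdrawal clause.** Protocol 3.4.2 prohibits intranasal corticosteroids, and oral or intranasal decongestants apart from a short course or one-time procedural use. It ends: "Participants who received prohibited medications will be considered to have a protocol deviation and may require withdrawal from the study". The short course is defined in Protocol 3.4.1 as oxymetazoline for "a maximum of 3 consecutive days and a total maximum of 10 days during the treatment period". Use within that allowance is not affected by this point.

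**The estimand.** Protocol Table 1 (section 2.2.1) applies treatment policy to any decongestant use. For INCS it says: "If the use of INCS occurs in violation of the protocol, a treatment policy strategy will be used". SAP Table 5 (section 3.4.1) puts decongestant use, INCS use and early termination of study treatment in one category, also under treatment policy. SAP 3.4.2 carries the same estimand attributes to the first two key secondary endpoints.

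**Discontinuation.** The list in Protocol 3.5.10 opens with "Participation in the study treatment may be discontinued for any of the following reasons". In its prohibited-medication bullet, however, the investigator, in consultation with the sponsor and medical monitor, "will decide on a case-by-case basis whether the subject may continue in the study". The closing paragraph returns to treatment: "Subjects who withdraw or are withdrawn from the study treatment will be requested to return to the clinic".

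**Deviations.** Protocol section 8 sets a default, "All participants with protocol deviations will continue to be followed for safety and performance assessments", and then an exception, "unless sponsor determines that the participant should be discontinued from the study".

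**Retention and missing data.** Protocol 3.5.8 and 9.3.3 and SAP 3.1.8.3 encourage continued ePRO or use later data after early stopping of treatment. The window rule in SAP 3.1.2.1 is written for participants who stop treatment, or who finish the treatment stage without entering the extension. SAP 3.4.1.1 handles missing scores by MMRM under MAR.

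**The concern.** Treatment policy works only if scores are collected after the intercurrent event. Here the event is also a stated ground for possible removal from the study, after which nothing requires 3CS collection. The retention text covers stopping treatment, not being withdrawn from the study.

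A withdrawn user's missing Week 24 score is then predicted from comparable participants under MAR. If withdrawn sham users would have scored better than that prediction, the estimate favours LYR-210. If they would have scored worse, it favours sham. For withdrawn LYR-210 users the directions reverse.

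Withdrawal may also differ by arm. Protocol 3.5.4 leaves the treating investigator unblinded, and 3.5.10 gives the investigator a part in the decision. The documents do not say which investigator this is. Sponsor blinding reduces the risk without excluding it.

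**Working it through.** **1. Does other text close the gap?** Section 3.5.10 is headed as treatment discontinuation, but its relevant bullet concerns staying in the study. Section 8 makes follow-up the default but lets the sponsor end it. The remaining provisions start from stopping treatment. Withdrawal from the study therefore stays open.

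Two other sections show that the protocol can state retention plainly. Protocol 3.7.12 keeps systemic corticosteroid users on study treatment and visits. Protocol 7.8 continues follow-up to Week 24 after a pregnancy in the treatment phase. The result is uneven: steroid rescue users, whose later scores are replaced by imputation, have explicit retention, while INCS users, whose later scores are needed, can be withdrawn.

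**2. The plan's own figure.** SAP 2.2.4 gives 50 control and 100 LYR-210, alpha 0.05 (two-sided, SAP 3.1.6), effect size 0.63, difference 1.31 and power 0.95.
- Implied SD = 1.31 / 0.63 = 2.08.
- SE of the difference = 2.08 × √(1/50 + 1/100) = 0.360.
- Power = 0.953 by the normal approximation and 0.951 by noncentral t. The stated 0.95 is reproduced.

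**3. Shift in the treatment difference.** Let kS and kL be the numbers withdrawn from sham and LYR-210. Let g be the MAR-predicted Week 24 score minus the score that would have been reported. For a common g, the error in (sham minus LYR-210) is

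(kS/50) × g − (kL/100) × g,

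with a positive value favouring LYR-210. Each sham participant moves the difference by 1/50 = 0.02 per point of gap, and each LYR-210 participant by 1/100 = 0.01 the other way. The documents give no rates, so every k and g below is an assumption.

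| Assumed withdrawals and gap | Calculation | Shift | Share of 1.31 |
|---|---|---|---|
| 3 per arm, g = 0.5 | (0.06 − 0.03) × 0.5 | 0.015 | 1.1% |
| 5 per arm, g = 1.0 | (0.10 − 0.05) × 1.0 | 0.05 | 3.8% |
| 5 sham, 0 LYR-210, g = 1.0 | 0.10 × 1.0 | 0.10 | 7.6% |
| 5 per arm, gaps of 1.0 with opposite signs | 0.10 + 0.05 | 0.15 | 11.5% |
| 15% of sham, 5% of LYR-210, g = 2.0 | (0.15 − 0.05) × 2.0 | 0.20 | 15.3% |
| Equal shares, equal gaps | cancels | 0 | 0% |

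Reversing the sign of g reverses each shift. The 0.10 case is 0.10 / 0.360 = 0.28 of the design SE.

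**4. Scores reported before withdrawal.** These stay in the model and shrink the shift. As an illustration, take six earlier visits (Weeks 2 to 20 in SAP Table 1a), with only the last one after use and showing the same gap, and an assumed correlation of 0.6.
- Compound symmetry: weight on that visit = 0.6 / (1 + 5 × 0.6) = 0.15, so 0.85 of the gap remains.
- First-order autoregressive: weight = 0.6, so 0.40 remains.

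The 0.10 shift becomes 0.085 or 0.04. Other withdrawal times give other fractions. A participant withdrawn after the Week 24 window opens at Day 148, with a valid weekly score in it, loses nothing.

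**5. Precision.** Losing 5 per arm and ignoring all earlier visits leaves 45 and 95. The SE becomes 2.08 × √(1/45 + 1/95) = 0.376, a ratio of 1.045. Power at 1.31 falls from 0.951 to 0.933 (noncentral t). This is a worst case for that number lost, because the MMRM uses the earlier visits.

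**The case against.** The strongest reply is that the plan already leans towards retention. The clause is permissive, section 8 makes continued follow-up the rule for all deviators, and 3.5.10 sits under a heading about study treatment. Where the protocol means removal from the study, as for sinonasal surgery in 3.7.13, it says so directly. The discretion also has a proper purpose: the same sentence covers potent CYP3A4 inhibitors, monoclonal antibodies and oral antifungals, and 3.5.10 ties the decision to timing and pharmacology. Finally, the tipping-point analysis in SAP 3.4.1.2 covers shifts of up to 9 points, well beyond the gaps assumed here.

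Most of this stands as a limit on severity. Few participants are likely to be affected, and nothing suggests that INCS or decongestant users would be withdrawn routinely. It does not remove the conflict. The default has an explicit exception, and the bullet in 3.5.10 speaks of the study. Safety discretion can be kept by directing it at study treatment. The tipping-point analysis tests how fragile the result is but cannot restore scores that were never collected. Nor is withdrawal needed to protect the analysis: important deviations are already excluded from the per-protocol set (SAP 3.2.3), which has its own supplementary analysis (SAP 3.4.1.3).

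**Conclusion.** The concern holds. A discretionary clause can stop the collection of scores on which the primary estimand is defined, and no other text rules that out. The bias is probably small and its direction cannot be known in advance. With up to five withdrawn per arm and a common gap of up to one point, the shift is at most 0.10 points against a design difference of 1.31, and it is zero when shares and gaps are equal. Only deliberately heavy assumptions reach 0.15 to 0.20. Losing five per arm leaves power at 0.933 or more. All of these figures rest on assumed withdrawal numbers and gaps, because the documents give none. The change should be made because it is cheap and aligns trial conduct with the estimand, not because a large bias is expected.

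**What to change.** Amend Protocol 3.4.2, 3.5.10 and section 8 to say that:
- use of a prohibited medication is recorded as a deviation and is not by itself a reason for withdrawal from the study;
- any resulting action concerns study treatment only, with clinical judgement on treatment unchanged (for example with potent CYP3A4 inhibitors or monoclonal antibodies);
- daily 3CS ePRO, SNOT-22 and scheduled visits continue to Week 24 unless the participant withdraws consent.

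The cost is a short wording amendment in three sections and a memo to sites. The assessments are already in the schedule (Protocol Appendix 14.1). The downside is a few more follow-up contacts.
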